The Combined Portfolio Diet and Exercise Study (PortfolioEx)

NCT 02481466

Protocol - September 2, 2022

Name of Nominated Principal Applicant	(V21) September 2, 2022
[name]	
Full project title	
MRI – Enhanced Dietary Portfolio plus Exercise on Cardiovascular Risk	

Combined Study Protocol

Protocol

12B) PROPOSED TRIAL

12B) I. What is the proposed trial design? This is a randomized 2x2 factorial design with four experimental arms of 3 years duration (Figure 2) to estimate the effect of the enhanced dietary portfolio, with or without increased physical activity under real world conditions. Participants will be recruited in 3 academic centers in 3 cities across Canada (Quebec, Toronto, Vancouver) from newspaper advertisements providing they do not require pharmacological intervention according to current CCS guidelines (1) and are within 30% of their target LDL-C concentrations for the low or moderate risk category according to current Canadian Working Group recommendations (2), i.e. those who would normally be considered for initial treatment with lifestyle alone. All participants will first be screened by ultrasound for the presence of plaque in the carotid arteries and will then be randomized to one of the four experimental arms:

[figure not shown]
- 1) enhanced dietary portfolio (Appendix 4- Table 1) and an intensive increased physical activity program with follow up at 3-month intervals for the remainder of the trial,
- 2) enhanced dietary portfolio and a copy of Health Canada Physical Activity Guidelines with advice to increase physical activity
- 3) control diet (modified DASH, Appendix 4- Table 2) given as routine clinical advice as used in our recent studies (JAMA 2008, 2011) (3, 4) and an intensive increased physical activity program with follow up at 3 month intervals for the remainder of the trial
- 4) control diet (modified DASH) as described in (3) above and a copy of Health Canada Physical Activity Guidelines with advice to increase physical activity.

[name]

Full project title

MRI – Enhanced Dietary Portfolio plus Exercise on Cardiovascular Risk**Combined Study Protocol**

Figure 2: Schematic Design of Combined Study

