The kinesiologist will work with participants in the structured exercise arms using behavioral strategies to develop and support a plan that aims to achieve the target of 150 min/week of physical activity or exercise in 3 or 5 sessions weekly (vigorous, moderate or mild depending of goals and tolerance) in keeping with maximum achievable goals of participants (19). When necessary, appropriate walking speed/intensity will be demonstrated on a treadmill by the kinesiologist. The program will also target a goal of achieving at least 10,000 steps daily recorded on their pedometers. We expect from previous experience that the vast majority of participants will have a much lower step count than the 10,000 step target at baseline but that most of them will be able to reach this target within 3 months (20). The routine exercise groups will receive standard of care for individuals being seen by a general practitioner. Specifically they will be advised to achieve the current recommended targets for daily physical activity and educational material published by Health Canada (Canada's Physical Activity Guide, Health Canada, Please see Appendix 4). Participants in the routine exercise arms will receive an exercise diary and the 7-D diet histories including the treadmill tests at the start and end of each 1 year period. They will not receive the more frequent, targeted visits with a certified kinesiologist.

12B) III. What are the proposed practical arrangements for allocating participants to trial groups? Participants who meet inclusion criteria will be randomized after stratification by centre and sex, due to the later onset of CHD in women. Random permuted blocks of varying

Name of Nominated Principal Applicant	(V21) September 2, 2022
[name]	
Full project title MRI – Enhanced Dietary Portfolio plus Exercise on Cardiovascular Risk	

Combined Study Protocol

sizes (≤ 10) will be used to eliminate the possibility of predicting a future allocation leading to selection bias. The treatment allocation will be revealed to the dietitian using the web-based system after stratum entry, in the presence of the participant during the zero time visit.

12B) IV. What are the proposed methods for protecting against other sources of bias?

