Blinding or masking the participants or the dietitians in this study is not possible due to the very different nature and physical form of the foods. The statistician will be blinded to the nature of the treatment when analyzing the data (i.e. will not know what treatment assignment 1 and 2 refer to). Physicians will not be informed of patient randomization when requested to make clinical decisions. Technicians who measure study outcomes will be blinded to the treatments, as will those who will be scoring the MRI images at the central location. It will be stressed to the participants that both dietary treatments have been considered to confer benefits. In this way the expectation of benefit from either treatment will be balanced (equipoise) (Please also see section 12B) I.).

12B) V. What are the planned inclusion/exclusion criteria?

Inclusion criteria: (Please also see 12 B) I for basic inclusion criteria) Eligible participants will be men and postmenopausal women with a $BMI \leq 40 \text{ kg/m}^2$ and who have measurable arterial thickening ($>1.2\text{mm}$) at screening (please see details of risks, Sections 12A) and 12B) I). They should also have at least 1 of the following characteristics:

- Type 2 diabetes;
- Non-diabetic subjects post MI or post percutaneous coronary intervention (angioplasty) on statin therapy;
- Hypercholesterolemic and treated with statins or have been prescribed statins but are not taking it because of either statin intolerance or have refused statin treatment.
- Raised blood pressure ($>140/90$ untreated)

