12B) VII. What is the proposed frequency and duration of follow-up? (Please see section 12B) I. and Figure 2) The MRI imaging assessment of carotid arteries will be done at baseline, year 1 and year 3. Previous assessments using the 1-3 year time frame for angiographic and MRI assessments of diet (22-24) and statin trials have shown benefits (25-27) which have increased over time (28). An assessment of recruitment and retention will be made at 1 year for future grant writing and as progress report for CIHR.

12B) VIII. (a) What are the proposed primary and secondary outcome measures?

Primary: Maximum Vessel Wall Volume by MRI at years 1 and 3.

Secondary: Lipid rich necrotic core and intra plaque hemorrhage assessed by MRI at years 1 and 3; blood pressure and pulse rate at year 3; and treatment difference in initiation of statin therapy according to current CCS guidelines (1).

Tertiary: Completeness of clinic attendance (and data collection) and provision of treadmill testing, exercise histories, and pedometer records and change in formal measures of physical activity including heart rate on standardized testing. Changes in fitness/daily step counts will also be recorded (see methods below (12b-IX).

12B) VIII. (b) What is the justification for the primary and secondary outcome measures?: Primary and secondary outcomes should relate to preclinical CHD, be non-invasive, not involve ionizing radiation, and allow conclusions to be drawn from small sample sizes in finite periods of time. We believe that MRI the imaging techniques fulfill these criteria.

12B) IX. How will the outcome measures be measured at follow-up?

Diet Recording Methods: All subjects will be instructed on diet history recording and also supplied with printed booklets in which to record food items and their amounts, either as actual weights or amounts using common measures e.g. cups or teaspoons etc., during the periods when diet histories are recorded (29, 30).

Physical activity/Exercise tolerance (or cardiorespiratory fitness): Physical activity will be assessed using a waist mounted pedometer collected over a period of 7 days every month for the first 12 months of the trial. As mentioned previously cardiorespiratory fitness will be assessed using a sub-maximal treadmill test annually. A standardized 7 day physical activity journal will also be recorded and continuous pedometer recording for the year on the test, and at the start and end of the year only (31) for the control.

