We have selected -106.5mm^3 as the effect size treatment difference at year 3 in MRI assessed plaque volume based on a study by Migrino et al. that demonstrated a reduction in plaque volume following increased statin dosage (36). This study demonstrated a 60mm^3 reduction in plaque volume for a 0.31mmol reduction in LDL-C (36) over a 6-month period. Our own recent portfolio study (**JAMA 2011**) demonstrated a 0.49mmol/L LDL-C reduction at 6 months on the portfolio arm after allowance was made for 0.16mmol/L LDL-C reduction on the control. Our planned study will last for 3 years and our unpublished open label single phase dietary portfolio study of 61 participants indicated a further reduction of 0.06mmol/L in LDL-C over the 6 month to 3 year period. We have added this further reduction to our JAMA 2011 value (4), giving an overall 0.55mmol/L LDL-C reduction. This 0.55mmol/L LDL-C reduction would correspond to a between treatment difference of 106.5mm^3 in plaque volume, according to the findings of Migrino and colleagues and therefore will be our effect size (36).

ii) SD was determined to be 276mm^3 by using a pooled SD from the Migrino paper (baseline: 300mm^3 , end of treatment: 331m m^3 , $n=26$) (36), a [name] cross-sectional assessment (210mm^3 , $n=10$) (37), and our own preliminary data from our CIHR diabetes study at baseline and 1 year (baseline: 227mm^3 , 1-year: 225mm^3 , $n=16$) (pooled data, blinded to treatment). We used the two papers since they assessed individuals with more modest plaque, similar to the population to be recruited. These SDs spanned the range of SDs emerging from our current CIHR funded glycemic index MRI study.

iii) Dropout: Our recent portfolio diet study had a dropout rate of 23% (**JAMA 2011**) (4). However, our current CIHR funded low GI diet study with similar ultrasound and MRI protocol has only had a 10% (7/69) dropout in the 1-year period (6/7 dropped out in the first 3 months). We therefore consider our dropout rate will be between 10% and 25% and most likely below 20% (i.e. >80% retention), which has traditionally been considered as providing a high level of evidence, e.g. National Institute for Health and Clinical Excellence (NICE), Grading of Recommendations Assessment, Development and Evaluation (GRADE), etc (38-41). However, we have allowed for 30% dropout in the sample size calculation to ensure that we have adequate power.

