a. 12B) XV. How many centres will be involved? Three recruitment sites will be involved: Institute of Nutraceuticals and Functional Foods, Laval University, Quebec; Healthy Heart Lipid Clinic, St. Paul's Hospital, Vancouver; and the Clinical Nutrition and Risk Factor Modification Centre, St Michael's Hospital or the David Naylor Building at the University of Toronto, and North York Family Health Team, North York General Hospital will be the recruitment clinics in Toronto. The MRI unit, Sunnybrook Health Science Centre, Toronto, Ontario, will be responsible for the interpretation of MRI scans. Robarts Institute, Western University, will be interpret and analyze screening US data. The Department of Biostatistics, McMaster University will oversee statistical aspects of the trial. The Nutritional Sciences Department, Faculty of Medicine, University of Toronto will also be involved in the assessment and quality control of recorded dietary data for all centres. We are adding an additional stress test clinic site, Toronto Cardiac Clinic because the stress test clinic at St. Michael's Hospital is not able to accommodate all of our research study patients because of the Covid-19 pandemic. Participants randomized (as opposed to screened) will be 98 at the Toronto site and 48 each at the other sites.

12B) XVI. What is the proposed type of analysis? An ANCOVA linear regression model will be used with the 3 year value as the outcome, treatment and sex as main effects and baseline as a covariate. In the intention-to-treat analysis, we will assume that data are multivariate, normally distributed and missing data are missing at random (MAR). For multiple imputations, the mean of 5 sets of generated data will be taken; this process will generate data for missing values, standard errors, and 95% confidence intervals [CI]. For example, using LDL-C

Name of Nominated Principal Applicant	(V21) September 2, 2022
[name]	
Full project title MRI – Enhanced Dietary Portfolio plus Exercise on Cardiovascular Risk	

Combined Study Protocol

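### The stated primary model has one undefined treatment term in a diet-by-exercise factorial, so no exercise or combined contrast on vessel wall volume is stated

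*Protocol*

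**What the plan says.** Protocol section 12B) I describes the design: "This is a randomized 2x2 factorial design with four experimental arms of 3 years duration", "to estimate the effect of the enhanced dietary portfolio, with or without increased physical activity under real world conditions". The four arms cross two diets with two levels of exercise support. The project title reads "Enhanced Dietary Portfolio plus Exercise on Cardiovascular Risk". Section 12B) III says that participants "will be randomized after stratification by centre and sex".

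Section 12B) XVI gives the only stated primary model, an ANCOVA "with the 3 year value as the outcome, treatment and sex as main effects and baseline as a covariate". It does not say whether treatment means diet, exercise, both factors or the four arms. Centre is not in the model.

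Four other places bear on the meaning of treatment:
- Section 12B) IV: the blinded statistician "will not know what treatment assignment 1 and 2 refer to", which implies two levels.
- Section 12B) XI i): the effect size of 106.5 mm³ is derived from LDL-cholesterol changes on the portfolio diet. No exercise effect is given.
- Section 12B) XI v): an existing two-group calculation is carried over on the assumption of no interaction. Here diet and exercise are referred to together as two treatments.
- Section 12B) VIII (a): exercise features only in tertiary measures such as treadmill testing, step counts and fitness.

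The Trial Significance paragraph says that a favourable result on the primary outcome would encourage clinical use of diet and exercise in combination.

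**The concern.** A factorial design randomises two factors so that each can be estimated from all participants. A protocol that writes out its primary model with a single unlabelled treatment term does not say which factor is tested. It also leaves unclear whether the other factor will be reported on the primary outcome.

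Two things are at stake. First, the exercise comparison on vessel wall volume, for which the data are already being collected, may be left unreported or may be chosen after the fact. Second, a diet main effect is an average over both exercise levels. It does not show that exercise adds anything, and it does not estimate diet plus exercise against neither. A positive diet result could still be presented as support for the combination, because the significance paragraph already describes it that way.

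**Working it through.** **Inputs.** Difference 106.5 mm³, SD 276 mm³, alpha 0.05 (two-sided reproduces the stated figures), power 0.80, baseline correlation 0.6, dropout 30% and 194 randomised are all from section 12B) XI. The revised total of 260 is from section 12B) XII (a).

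**The plan's own figure.**
- t-test: 2 × [276 × (1.960 + 0.842) / 106.5]² = 105.4 per group (stated: 105).
- ANCOVA: 105 × (1 − 0.6²) = 67.2 (stated: 67).
- Dropout: 2 × 67 / 0.7 = 191.4 and 2 × 68 / 0.7 = 194.3 (stated: 194).

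The 194 therefore reproduces only as a comparison of two groups of about 97, which is one factor at the margins. (The 81 per arm printed beside it fits neither two nor four groups: 81 × 2 = 162 and 81 × 4 = 324. That is a separate matter.)

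**Reading 1: treatment is diet at two levels.** Residual SD = 276 × √0.64 = 220.8. SE of a main effect = 220.8 × √(4/n).
- 194 randomised: n = 194 × 0.7 = 135.8, SE 37.9, 95% CI half-width 75 mm³, power 79.7%.
- 260 randomised: n = 260 × 0.7 = 182, SE 32.7, half-width 65 mm³, power 89.9%.

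The diet test does what the plan says. An exercise main effect would have the same SE, but none is stated.

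**Reading 2: treatment is the four arms.** Exercise is then estimable, but no contrast is named. For a diet-only effect of 106.5 mm³, the 3-df F test has noncentrality 135.8 × (53.25)² / 220.8² = 7.9 and power of about 63% at 136 completers.

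**Reading 3: treatment is shorthand for both factors.** An exercise term is then present, but which factor is primary and which contrast represents the combination are still unstated.

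**Precision of the unstated contrasts at 182 completers (45.5 per arm).**
- Exercise main effect: SE 32.7, half-width 65 mm³.
- Arm 1 against arm 4: SE = 220.8 × √(2/45.5) = 46.3, half-width 91 mm³.
- Diet-by-exercise interaction: SE = 220.8 × √(4/45.5) = 65.5, half-width 129 mm³, which is too wide for more than description.

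**Power of arm 1 against arm 4.** This depends on an exercise effect that the documents do not give.
- Exercise assumed to add nothing (combined 106.5 mm³): about 63% at 260 randomised, 51% at 194.
- Exercise assumed to add 53 mm³ (combined about 160 mm³): about 93% at 260.
- Exercise assumed to add 106.5 mm³ (combined 213 mm³): over 99% at 260.

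**Cost of leaving terms out, 182 completers.**
- Exercise: diet power is 88.2% rather than 89.9% if the exercise effect is assumed to be 106.5 mm³.
- Centre: if it is assumed to explain a share p of residual variance, the true type I error is P(|t| > 1.973/√(1 − p)). This is about 4.4% for p = 0.05 and 3.9% for p = 0.10, so the error is on the conservative side.

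**Cost of adding them.** The model goes from four parameters to seven (exercise 1, centre 2). Diet power is 89.9% either way.

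**The case against.** The strongest reply is that the protocol's stated aim is the effect of the portfolio diet with or without exercise, and the marginal diet contrast answers exactly that. No section sets an objective of estimating exercise on vessel wall volume. The significance paragraph is grant-style rationale with no decision rule. A statistical analysis plan, not at hand, may define the term and name further contrasts.

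Much of this stands. The aim justifies keeping diet as the sole primary question. Interaction models and secondary contrasts are often left to the analysis plan. What remains is that the protocol does write out its model, and does so with a term that is ambiguous in a two-factor trial. Its significance paragraph also attaches to the primary outcome a conclusion that the model does not address.

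A reader might go further and infer that the exercise randomisation yields no estimate at all, or that half the factorial is wasted. The documents do not support that. Treatment is undefined, section 12B) XI v) applies the word to both factors, and exercise-arm participants contribute fully to the diet contrast. Nor can one infer that the combined contrast is adequately powered and merely unreported: that holds only under an assumed exercise effect.

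**Conclusion.** The point holds as a fault of specification that should be fixed. It is not a source of bias. The diet contrast is unbiased, with about 80% power at 194 randomised and 90% at 260, given the plan's SD, correlation and 30% dropout. Exercise has no stated estimate on the primary outcome under the likeliest reading and no named contrast under the four-arm reading. Under every reading, the conclusion about the combination has no stated contrast behind it.

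That the term means diet is an inference from context. All figures assume equal arms and equal dropout, and those for exercise effects and for centre rest on the assumed values shown.

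Leaving out centre is conservative and small. It is worth adding because randomisation was stratified by it. Two wording points carry no weight here. The outcome list says "Primary: Maximum Vessel Wall Volume by MRI at years 1 and 3", but the effect size is set "as the effect size treatment difference at year 3 in MRI assessed plaque volume" and sections 12B) XVI and XVII also use year 3. The two-level blinding code would need one code per factor once both factors are in the model.

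**What to change.** In section 12B) XVI, state the model as: year-3 maximum vessel wall volume = diet + exercise + baseline + sex + centre. Name the diet main effect as primary and the exercise main effect as secondary, each with a 95% CI. With exercise secondary, no alpha split is needed; two co-primary independent tests at 0.05 would have a family-wise error of 1 − 0.95² = 0.0975. Report the diet-by-exercise interaction with its 95% CI from a separate model, labelled descriptive.

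In the Trial Significance paragraph, do one of two things. Either limit the conclusion to the factor tested, or report the arm 1 minus arm 4 difference with its 95% CI from the model that includes the interaction. That model should be specified because the sum of the two main effects equals the arm 1 minus arm 4 difference exactly only with balance. After dropout the two can differ, and the sum assumes no interaction. Claim no power for the combined contrast.

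The cost is wording plus three model degrees of freedom (one more in the interaction model). Diet power changes by less than 0.1 point. No new data or participants are needed.

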on a cycle ergometer (9). The protocol begins with a warm-up workload of 2.5 mph with a 0% slope. The second stage is performed at a speed of 3.5 mph with a 2% slope. The third stage is adjusted in an attempt to reach 75% of the age-estimated maximal heart rate (HR). If necessary, a 4th stage is performed. Estimated VO₂max is predicted by extrapolation to age-predicted maximal heart rate (DHR at a standardized submaximal treadmill stage (3.5 mph, 2% slope) and estimated maximal oxygen consumption (VO₂max) are the variables considered as indicators of CRF in the present study. For treatments with routine advice to increase physical activity Health Canada Physical Activity Guidelines for adults 18-64 years or for older adults 65 years & older will be provided. They will be seen at the start and the end of each year for their formal exercise testing and will bring with them completed physical activities questionnaires. They will receive no other physical activities instruction. Prior to starting either diet, participants will undergo screening ultrasound examination of both right and left carotids to enable selection of those individuals whose intima-media thickness (IMT) would be 5-30% below the cut point considered by the Mannheim Consensus (10) as relevant arterial thickening to ensure a relatively low risk group, yet with some measurable arterial thickening. The **main outcome** will be **MRI** assessment of maximum vessel wall volume. This assessment will be repeated at year 1 and 3. It will be emphasized at the outset that both the dietary portfolio (11-14) and the DASH-like diets (15, 16) have been associated with benefits in terms of cholesterol reduction to provide equal encouragement for those randomized to the test and control groups. Portfolio and DASH-like dietary advice will consist of half hour individual sessions with the dietitian at baseline, and at 3-month intervals throughout the trial. Prior to starting each diet, instruction will be given on achieving the dietary goals. Visits or telephone calls to reinforce dietary advice and optimize retention will be conducted at 2 weeks and 4 weeks after randomization. At subsequent follow-up visits, the participants' completed 7-day diet records will be discussed and the original advice will continue to be reinforced. Every effort will be made to obtain study blood samples and carotid imaging data from all subjects at the designated times regardless of adherence to the dietary aspects of the study protocol. All subjects will be included in the intention-to-treat analysis.

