at 24 weeks in our recent study, the strongest predictors of missingness at 24 weeks were age ($\beta = 0.0454, P = .01$) and sex (women vs. men) ($\beta = -0.2807, P = .11$) (4), and these, along with the observed values, were used to inform the imputations. Site and diet assignment did not predict missingness in that study ($P \geq .16$) (4). As a sensitivity analysis, we will compare the results using the ITT with those of the completers-only. The 10-year Framingham CHD risk score will also be calculated (53) for this predominantly white cohort. Pearson correlation will be used to calculate the correlation coefficient between dietary adherence and change in maximum vessel wall volume (plaque volume).

12B) XVII. What is the proposed frequency of analyses? The imaging analyses will be made at baseline and year 3. Assessment of recruitment and retention will be made at 1y to inform further grant applications

12B) XVIII. Are there any planned subgroup analyses? No subgroup analyses are planned. However, we may conduct exploratory analyses by sex, site, or within groups meeting specified LDL-targets. Since we are not primarily powered for these analyses, we will treat these as secondary, exploratory analyses only.

12B) XIX. Has any pilot study been carried out using this design? A number of dietary portfolio studies (12) including the CIHR funded study of 6 months duration have now been completed (**JAMA 2011**) (4) demonstrating 13-14% LDL-C reductions with 40% adherence to all the recommended dietary components which are the same as those being tested in present study. Similarly, our CIHR funded low glycemic index study (**JAMA 2008**) (3) and our CIHR monounsaturated fat enriched portfolio study (**CMAJ 2010**) have also provided feedback (54). These studies have influenced the design of the present study in terms of power, magnitude of expected effect, and dropout rate, together with considerable feedback on participants' dietary preferences to facilitate overall adherence. The exercise protocol has been tested successfully in participants at high risk of CVD (55).

12C) TRIAL MANAGEMENT

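### The multiple-imputation sentence averages five generated data sets instead of pooling five analyses; followed literally it gives an invalid intention-to-treat interval, and the form of the error depends on whether assignment is in the imputation model

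*Protocol*

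**What the plan says.** Section 12B) XVI makes the primary analysis an ANCOVA of the 3-year value on treatment, sex and baseline. Missing data are taken as multivariate normal and missing at random. The imputation rule is: "For multiple imputations, the mean of 5 sets of generated data will be taken; this process will generate data for missing values, standard errors". The confidence limits come from the same step.

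The section then describes an earlier study as the example. Its imputations were informed by age, sex and the observed values. Whether the randomised assignments enter the imputation model, there or here, is not stated. A further check is planned: "As a sensitivity analysis, we will compare the results using the ITT with those of the completers-only".

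On the amount of missing data, section 12B) XI iii) says "We therefore consider our dropout rate will be between 10% and 25% and most likely below 20" per cent, and then "we have allowed for 30% dropout in the sample size calculation to ensure that we have adequate power". Of the dropouts in a related study it notes that "6/7 dropped out in the first 3 months". On scans, section 12B) VII says "The MRI imaging assessment of carotid arteries will be done at baseline, year 1 and year 3", and section 12B) I says "Every effort will be made to obtain study blood samples and carotid imaging data from all subjects at the designated times regardless of adherence".

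**The concern.** In multiple imputation the analysis is run in each completed data set. The estimates are then averaged, and the variance is the mean within-imputation variance plus the between-imputation variance. The protocol's sentence averages something else, the generated data, and has the same process supply the standard errors and intervals.

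Averaging five draws removes most of the noise from each imputed value, and a single ANCOVA then counts those smoothed values as observations. The reported standard error falls as scans are lost, when it should rise. The sentence governs the primary intention-to-treat result, so both the main confidence interval and the main test are affected.

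**Working it through.** **Inputs.** Effect 106.5 mm³, SD 276 mm³, correlation 0.6, alpha 0.05 (taken as two-sided) and N=194 from 12B) XI; N=260 from 12B) XII (a); missing fractions d of 10–25% (expected) and 30% (planning) from 12B) XI iii); M=5 imputations from 12B) XVI.

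**The plan's own figures.** Two-sample t-test: 2 × (1.96+0.84)² × 276²/106.5² ≈ 105.4 per group (protocol: 105). Times (1−0.6²) = 67.5 (protocol: 67). With 30% dropout, 2×68/0.7 = 194.3 (protocol: 194). The planning inputs therefore reproduce. With no missing data, the SE of a main effect at N=194 is 276 × √0.64 × √(4/194) = 31.7 mm³.

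**Case 1: assignment in the imputation model, year-1 MRI not used.** In units of the complete-data variance:
- reported by the averaged set: (1−d) + d/5
- true: (1+d/5)/(1−d)
- type I error: 2 × [1 − Φ(1.96 × √(reported/true))]

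| Missing | Reported factor | True factor | Reported SE | True SE | SE ratio | Type I error | Simulated |
|---|---|---|---|---|---|---|---|
| 10% | 0.920 | 1.133 | 30.4 | 33.8 | 0.90 | 7.7% | 7.1–8.2% |
| 20% | 0.840 | 1.300 | 29.1 | 36.2 | 0.80 | 11.5% | 11.0–12.1% |
| 25% | 0.800 | 1.400 | 28.4 | 37.5 | 0.76 | 13.8% | 13.7–14.9% |
| 30% | 0.760 | 1.514 | 27.6 | 39.0 | 0.71 | 16.5% | 15.3–17.0% |

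SEs are in mm³ at N=194. The last column spans several simulations, some at N=260, using proper normal imputation and one ANCOVA on the averaged set. One smaller run, whose missingness came out above nominal, gave higher values (8.9% to 19.4%) and is left out. Coverage falls from about 92–93% at 10% missing to about 84% at 30%. Rubin pooling of the same imputations gave 4.2–5.6% throughout.

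**Case 1 with year-1 MRI known for everyone and used.** Let q be the residual variance of year 3 given baseline and year 1, divided by that given baseline alone. The reported factor becomes 1 − 0.8qd, and the true factor (1−q) + q/(1−d) + qd/[5(1−d)]. The correlations are assumptions (baseline to year 1 set at 0.6 to 0.8):

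| Year 1 to year 3 correlation | 10% missing | 25% missing |
|---|---|---|
| 0.9 | 5.7% | 7.2% |
| 0.8 | about 6.5% | about 9.5% |
| 0.7 | about 7% | about 11% |
| 0.6 | 7.3% | 12.4% |

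If 6/7 of dropouts lack the year-1 scan, as the early-dropout share in 12B) XI iii) suggests, little is gained. With a partial correlation of 0.7 assumed, simulated error was 7.1–7.7% at 10%, 10.7–11.0% at 20% and 12.8–12.9% at 25% missing.

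**Case 2: assignment not in the imputation model.** Imputed values then carry no treatment difference, so the expected estimate is about −106.5 × (1−d): −95.9, −85.2 and −79.9 mm³ at 10, 20 and 25% missing. Simulations gave about −95 to −96, −85 to −86 and −79 to −81. Type I error of the averaged-set test stayed at about 5–6%. Coverage under the planned effect: at 20% missing the bias is 21.3 mm³ against an SE of about 29.1, a ratio of 0.73, so coverage is Φ(1.96−0.73) − Φ(−1.96−0.73) ≈ 0.89. At 25% simulation gave about 86%.

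Rubin pooling without the assignments does not repair this case. The estimate stays attenuated, type I error drops to 1–3%, and power is about 60% at 25% missing.

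**The case against.** The strongest reply is that the sentence is shorthand. It opens by naming multiple imputation, and in ordinary practice the point estimate is also a mean over the five sets and the procedure does yield standard errors and intervals. It does not say outright that one ANCOVA is run on one averaged data set. A combining rule often sits in a SAP, which is not available here. This stands as a doubt about intent. It does not remove the problem, because the protocol states a procedure, the thing it averages is the data, and a SAP that repeated the sentence would carry the error forward.

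A reader might infer that the primary test will run at 7–14% over the expected dropout range. The documents do not support that. It needs both the literal reading and assignment in the imputation model, and the only predictors named, for the earlier study, are age, sex and observed values. Observed values does not exclude assignment, but nothing confirms it. Nor can a single range such as 6–10% be given once year-1 MRI is used, since it rests on a correlation the protocol does not supply.

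Other points stand in part. Dropout is expected to be below 20% (12B) XIV), and scans are sought regardless of adherence, so missing MRI may be lower than dropout. The completers-only comparison held its level in simulation (4.4–5.3%) and could expose a discrepancy, but it does not make the primary interval valid.

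**Conclusion.** The sentence should be corrected. Taken literally, it gives an invalid intention-to-treat interval in either case. With assignment in the imputation model the interval is too narrow and the test anti-conservative, at the rates in the first table. Without it the test keeps its level, but the estimate is biased towards no effect by roughly the missing fraction and the interval under-covers the planned effect.

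The figures assume data missing at random, the protocol's SD and correlation, and a percentage that counts missing year-3 scans and not dropouts as such. If ordinary pooling with assignment in the model was intended, the analysis is sound and only the wording is wrong.

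**What to change.** Replace the imputation sentence in 12B) XVI with: *Missing values will be multiply imputed from a model that includes the randomised diet and exercise assignments, sex, age, baseline and available year-1 MRI; the ANCOVA will be fitted in each imputed data set and the estimates and standard errors combined by Rubin's rules.*

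Both halves are needed: pooling restores the variance, and including the assignments prevents the attenuation.

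The change is one sentence and negligible computing. The price is a wider, valid interval. Compared with the averaged set (year-1 MRI not used), the SE is about 11% larger at 10% missing and 25% larger at 20% (29.1 to 36.5 mm³ at N=194; 25.2 to 31.4 at N=260, by simulation). Power for 106.5 mm³ with 20% missing is then about 80% at N=194 and 91% at N=260.
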